Safety Profile: Systemic and hematologic: Pioglitazone may be associated with hypoglycemia, edema, anemia (lower hemoglobin levels and hematocrit due to edema), weight gain (increased fat cell differentiation), and/or ovulation in premenopausal, anovulatory women. The most common adverse events (≥5%) reported to date include upper respiratory tract infection, headache, sinusitis, myalgia, tooth disorder, aggravated diabetes mellitus, and pharyngitis.

Gastrointestinal (GI)/Liver: Reports of hepatitis and of hepatic enzyme elevations to three or more times the upper limit of normal (ULN) have been reported with pioglitazone. Very rarely, these reports have involved hepatic failure with or without fatal outcome, although causality has not been established. Liver enzymes, including serum ALT, need to be evaluated in all patients at initiation of therapy with pioglitazone, and periodically thereafter. If ALT >2.5X ULN at baseline or if the patient exhibits clinical evidence of active liver disease, pioglitazone will be discontinued.

Systemic: Like other thiazolidinediones (TZDs), pioglitazone can cause fluid retention when used alone or in combination with other anti-diabetic agents, including insulin. Fluid retention may lead to or exacerbate heart failure. However, in the context of pancreatic cancer, these potential issues seem relatively minor. Nevertheless, we will exclude patients with a history of previously existing cardiac disease.

Cardiovascular: The Endocrinologic and Metabolic Drugs and Drug Safety and Risk Management Advisory Committees to the FDA recently met jointly to review the cardiovascular ischemic/thrombotic risks of the thiazolidinediones (TZDs) class, with focus on rosiglitazone. At this stage, there were no concerns raised with respect to the cardiovascular safety of pioglitazone.

Pioglitazone has been prescribed in many patients with pancreas cancer who have a diagnosis of type 2 diabetes mellitus in routine clinical practice. To our knowledge, no unexpected serious adverse events have been reported in patients with pancreas cancer receiving treatment with pioglitazone.

Table 1: Adverse Effects of Pioglitazone

Placebo-Controlled Clinical Studies of ACTOS Monotherapy: Adverse Events Reported at a Frequency ≥ 5% of Patients Treated with ACTOS

(% of Patients)		
Adverse Effects	Placebo N=259	ACTOS N=606
Upper Respiratory Tract Infection	8.5	13.2
Headache	6.9	9.1
Sinusitis	4.6	6.3
Myalgia	2.7	5.4
Tooth Disorder	2.3	5.3

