Diabetes Mellitus Aggravated	8.1	5.1
Pharyngitis	0.8	5.1

Rationale for the Selection of Dose and Schedule

We plan to prescribe pioglitazone 45 mg per mouth daily, which is the maximum U. S. Food and Drug Administration (FDA) approved dose for the treatment of type 2 diabetes mellitus. Pioglitazone has been extensively prescribed in humans at the planned doses for this study. The safety and toxicity profile of pioglitazone is well established. We do not expect a higher than usual toxicity in patients with pancreas cancer receiving pioglitazone.

IV. Schema

This is an open label, double arm Phase 2 study. We plan to enroll 15 patients with adenocarcinoma of the pancreas to this study of oral pioglitazone 45 mg daily. Patients are allowed to continue on antineoplastic therapy while on this study and this will be determined by the treating physician.

A control cohort of up to 10 patients will be enrolled for correlative (blood and radiological) testing alone. These patients will meet all criteria set forth for the study and follow the same study visits, but not be treated with pioglitazone.

V. Hypothesis

Prior studies have shown that a significant proportion of patients with metastatic pancreas cancer have metabolic changes consistent with insulin resistance. Treatment of insulin resistance in patients with metabolic disorders like type 2 diabetes mellitus is associated with improved outcomes and less morbidity. We propose an exploratory clinical trial to study as a primary aim, the effects of the oral inhibitor of the peroxisome proliferator- activated receptor gamma (PPAR γ) pioglitazone in markers of insulin resistance in patients with pancreas cancer.

Our primary hypothesis is that patients with pancreas cancer will have significant improvements in markers of insulin resistance when treated with pioglitazone.

As secondary aims, we will evaluate changes in cancer related symptoms, performance status, and weight. We will also evaluate the objective response of measurable lesions and the time to disease progression in patients with pancreas cancer. MRI will be used to assess for changes in body fat distribution and changes in intratumor fat content (UT Southwestern and PHHS patients ONLY). We will compare change in blood biomarkers and MRI between the pioglitazone and control arms.

VI. Objectives

Primary objective

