We plan to enroll fifteen patients with metastatic or locally advanced pancreas cancer into a double arm pilot exploratory study of oral pioglitazone 45 mg daily.

Treatment will be administered for 8 weeks and then stopped.

Control Arm:

Up to ten patients meeting eligibility criteria will be enrolled in the control arm. Patients will be treated per standard of care treatment at the discretion of the treating team and will not be treated with pioglitazone.

Treatment arm assignment:

Treatment arm will be assigned by the principal investigator or treating MD at their discretion. Given the exploratory nature of this study, randomization will not be performed.

Control arm patients can include the following examples:

- patient declines pioglitazone therapy but agrees to biomarker testing (Adiponectin, a hormone made by fat cells, will be measured). Additional assays may be performed
- Patient is enrolled in another clinical trial which does not allow experimental therapy (pioglitazone) to be given. The protocol of the patient's study will be reviewed to ensure biomarker testing (Adiponectin, a hormone made by fat cells, will be measured) as defined in this study is not specifically prohibited.

- Patients enrolled after completion of the 15 study arm patients
- Other patients as deemed appropriate by the PI or co-Is

A. Recruitment

Eligible study patients will be screened, recruited, and enrolled at the following institutions:

1. University of Texas Southwestern Medical Center at Dallas:
 - a. Harold C. Simmons Comprehensive Cancer Center
 - b. University Hospital – Zale Lipshy
 - c. University Hospital – Saint Paul
2. Parkland Health and Hospital System (PHHS)
3. VA North Texas (Dallas)

Study patients will be recruited from the practices of the PI and co- investigators. Potentially eligible patients will be approached by their health care providers who can refer them to the study coordinator for screening. All patients being considered for the study and eligible must sign an informed consent for the study prior to any study specific procedures.

IX. Eligibility Criteria

Inclusion Criteria

Inclusion Criteria	Reason
Signed informed consent	Document patient participation and understanding of study requirements
Histologically proven adenocarcinoma of the pancreas	Disease of interest
Radiologically measurable disease	Target lesion to follow response to therapy

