ECOG functional status 0-2	Those with worse functional status may not have reasonable survival to demonstrate meaningful follow up

Exclusion Criteria	Reason
Prior radiation therapy for pancreatic cancer	Radiation effect can alter metabolic effects of the pancreas. If patient has measurable disease which has not been radiated, they may be enrolled.
If chemotherapy is planned, new chemotherapy regimen should have started no more than 21 days prior to enrollment	Start pioglitazone as close to the start of a chemotherapy regimen
Surgery or radiation planned within 8 weeks of starting therapy	Allow adequate exposure to TZD (minimum 8 weeks)

Prior exposure to Thiazolidinedione (TZD) therapy in the past 12 months	Markers of interest will be altered by previous TZD exposure
Hypersensitivity of TZD	Contraindication to pioglitazone
New York heart association class III/IV heart failure.	Contraindication to pioglitazone
Known HIV positive	HIV/AIDS related cachexia may alter metabolic findings.
Pregnant or lactating women	Contraindication to pioglitazone. Pregnancy class C, not recommended in lactating women
History of, or active bladder cancer	Contraindication to pioglitazone
Inadequate hepatic function documented within 14 days of enrollment Total bilirubin level > 1.5 x ULN AST and ALT > 2.5 x ULN, unless there are liver metastases in which case AST and ALT or > 5 x ULN	TZD Clearance is significantly lower in hepatic impairment

X. Informed Consent Process

The research coordinator or the investigators will review the consent form with the subject page by page describing the purpose of the study, the research procedures, risks and alternatives. The subject will be given the opportunity to ask questions or voice concerns at this time. The informed consent counseling will take place in an area that provides privacy. The PI or co-investigator will describe all available options to potential patients, to answer questions, and to help the patients make participation decisions in a non-directive manner. The original signed informed consent document will be stored in a locked cabinet with the patient's case report forms (CRFs) in the Clinical Research Office (CRO), one copy will be given to the patient and one copy will be placed on the chart per institutional policy. Patients who are sedated or deemed emotionally or mentally unable to provide informed consent for any reason are not eligible for enrollment.

XI. Study Subject Identification Number

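### The Safety Profile text and the Section IX exclusion table give opposite answers on cardiac history and on baseline ALT, two rules that decide who may receive pioglitazone

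*Combined protocol and SAP*

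**What the plan says.** **Safety Profile (pioglitazone background).** On the heart, the text warns: "Fluid retention may lead to or exacerbate heart failure". It plays this risk down for pancreatic cancer, but then commits that "we will exclude patients with a history of previously existing cardiac disease". On the liver, it says: "Liver enzymes, including serum ALT, need to be evaluated in all patients at initiation of therapy with pioglitazone, and periodically thereafter". The next sentence is a rule: "If ALT >2.5X ULN at baseline or if the patient exhibits clinical evidence of active liver disease, pioglitazone will be discontinued". Liver metastases are not mentioned.

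**Section IX, exclusion table.** The single cardiac row is "New York heart association class III/IV heart failure". The hepatic row uses tests from the 14 days around enrollment. It excludes total bilirubin above 1.5 x ULN, and AST and ALT above 2.5 x ULN, "unless there are liver metastases in which case AST and ALT or > 5 x ULN". The last clause is garbled; I read it as a limit of 5 x ULN when liver metastases are present.

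**Section IV (Schema).** On the control cohort: "These patients will meet all criteria set forth for the study and follow the same study visits, but not be treated with pioglitazone".

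**Sections XI and XII.** A Clinical Research Manager registers each patient once eligibility is confirmed, on receipt of the consent signature page and a signed inclusion/exclusion worksheet. The worksheet is not in the document.

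**Later sections on liver tests.** Section XIII.B draws ALT on cycle 1 day 1 before dosing and attaches no action to the result. The liver rule in Section XIII.D is a hold for grade 3 or 4 elevations. Section XIV lists reasons to stop treatment, none of which is an ALT value.

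**The concern.** Both rules are safeguards that the protocol sets for itself. The cardiac one follows from the fluid-retention warning. For the hepatic one, Section IX gives reduced drug clearance in hepatic impairment as its reason. In each case the two texts can be applied to the same patient with opposite results.

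Three things are at stake: whether a given patient may receive the drug, what population the trial describes, and what counts as a protocol deviation. Someone with lesser cardiac disease enrolled under Section IX complies with the table and breaches the background commitment. Someone with liver metastases and ALT between the two limits can be properly enrolled and, by another sentence, should be off treatment from baseline.

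**Working it through.** No figure in the plan depends on this point, so the check sets the passages side by side.

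**1. Cardiac history**

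| Patient | Safety Profile | Section IX |
|---|---|---|
| No cardiac history | allowed | allowed |
| Cardiac disease short of class III/IV heart failure | excluded | eligible |
| Class III/IV heart failure | excluded | excluded |

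The middle row is the conflict. Section IX cannot be read as spelling out the background rule, because class III/IV heart failure is a narrower condition than any history of cardiac disease.

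**2. Baseline ALT with liver metastases** (multiples of ULN)

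| ALT | Safety Profile | Section IX |
|---|---|---|
| 2.5 or below | no stop | eligible |
| above 2.5, up to 5 | drug stopped | eligible |
| above 5 | drug stopped | excluded, if ALT alone is enough |

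Test values of 2.6, 3, 4 and 5 fall in the conflict row; 2.0 and 2.5 do not, and 5.1 is barred by both texts. Because Section VIII recruits metastatic as well as locally advanced disease, such patients are within the target population. The word discontinued suits a patient not yet dosed poorly and may mean not started; the conflict is the same either way.

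**3. Baseline ALT without liver metastases.** Section IX joins the two enzymes with *and*. If either enzyme suffices, ALT above 2.5 x ULN excludes the patient and the texts agree. If both must be raised, a patient with ALT above 2.5 and AST at or below 2.5 x ULN is eligible under Section IX, and the Safety Profile still stops the drug. The document does not say which reading is meant.

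**4. Does any other section resolve it?**
- Section XIII.B collects the value on which the Safety Profile rule would act, but says nothing about acting on it.
- Section XIII.D acts only at grade 3 or 4. The document does not give the grade boundaries, so I do not convert them to multiples of ULN.
- Section XIV has general items on intercurrent illness and on physician judgement. With the Section IX bilirubin limit, these cover the second trigger, active liver disease, only in part. None names it.
- No passage ranks Section IX above the background.

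**5. Sample size.** The Section XX.A calculation takes 15 patients, a change of 0.4, a standard deviation of 0.5 and a 0.05 significance level. Neither rule is an input.

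**6. Lesser, separate matters on weight**
- The Appendix 2 log sends the reader to section XIV-D, which does not exist; the dose rules are in XIII.D.
- The log calls for dose modification above a kg limit, apparently baseline x 1.1 (inferred from a flattened table). Section XIII.D instead uses grade 3 or 4 weight gain. How far these differ cannot be judged without the grade cut-offs.
- The general rule in XIII.D lifts a hold when the event itself improves; the weight-gain rule lifts it on improvement of peripheral edema.
- Section XVI promises weekly weights, or 8 over 8 weeks. The visits and the log give 4 on-treatment weights, at weeks 2, 4, 6 and 8.

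**The case against.** The best defence is that the Safety Profile is background narrative and Section IX is the operative text: it bears the eligibility heading, gives a reason for each row, and feeds a signed worksheet without which nobody is registered. That is probably how sites screen, and it makes the cardiac item look partly like a clean-up of the background. It does not dispose of the point. The background wording is a commitment, no passage subordinates it, and which version the worksheet carries is unknown. Precedence would not settle the ALT item in any case: that sentence governs treatment, and meeting the entry criteria does not switch it off.

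A second defence is that Section XIV leaves room for clinical judgement. It does, but discretion does not reconcile two fixed rules.

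Some stronger readings are tempting and are not supported:

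- **Cardiac imbalance between arms.** A reader might infer this from "Treatment arm will be assigned by the principal investigator or treating MD at their discretion". It would require the background rule to be applied to treated patients only, contrary to Section IV. The comparison of arms is in any case labelled exploratory.
- **Sites enrolling differently.** Three institutions recruit, but registration passes through one Clinical Research Manager. That limits inconsistent enrollment, although it would not reveal a patient refused before submission.
- **The whole trial is affected.** The rules apply to up to 15 + 10 = 25 patients, but that counts those screened under them, not those in a gap. Likewise, the ALT band being half of the permitted range (2.5/5) says nothing about how many patients lie in it.
- **The ALT conflict is confined to liver metastases.** The *and* wording leaves that open.

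**Conclusion.** The protocol contradicts itself on both rules, in current text, and neither redaction nor an amendment log explains it. The cardiac conflict covers any patient with cardiac disease short of class III/IV heart failure. The ALT conflict certainly covers patients with liver metastases and ALT above 2.5 and up to 5 x ULN, given the reading of the garbled clause stated above. It extends to isolated ALT rises without metastases if Section IX requires both enzymes to be raised.

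The document gives no basis for estimating how many patients are affected, and I claim no rate. The case for correction rests on two safeguards that give opposite answers for the same patient, not on any loss of power. The weight matters are minor; the trigger comparison among them is the least certain.

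**What to change.** The sponsor's clinicians should:

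1. Reconcile the Safety Profile with Section IX on cardiac history, on baseline ALT (including whether one raised enzyme or both are needed, and the garbled metastasis clause) and on active liver disease.
2. State each rule once, in Section IX for entry and in Section XIII for treatment, including what follows from the day-1 ALT. The background should then refer to those sections.
3. Check that the inclusion/exclusion worksheet carries the same wording.

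Separately and at lower priority: correct the section reference in Appendix 2, reconcile its weight trigger and the edema-based release with the rest of Section XIII.D, and reconcile the weekly weights in Section XVI with the two-weekly visits and log.

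The cost is amendment wording, a worksheet check and a corrected weight log. Whether eligibility narrows depends on which version the clinicians keep. No view is given here on which rule, threshold or dose is right.

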1. Describe change in markers of insulin resistance, including in adiponectin levels standard glucose tolerance test, and serum levels of insulin and glucose in patients with pancreas cancer receiving pioglitazone.

Secondary Objectives

1. To determine the tumor response by RECIST in patients with pancreas cancer receiving pioglitazone.
2. To describe changes in weight in patients with pancreas cancer receiving pioglitazone.
3. To describe changes in ECOG performance status in patients with pancreas cancer receiving pioglitazone.

4. To describe changes in symptoms and quality of life using the FACT-Hep scale, version 4 (see Appendix 4).
5. Compare change in blood biomarkers and MRI between the pioglitazone and control arms.

VII. Endpoints

We will assess the primary and secondary endpoints of the study as follows:

Primary End point

The primary end point will be improvement in insulin resistance markers:

- a. Change in serum adiponectin level. We will obtain serum levels of adiponectin at baseline and after 8 weeks of treatment with pioglitazone.
- b. Changes in standard glucose tolerance test. We will perform the area under the oral glucose tolerance test at baseline and after 8 weeks of treatment with pioglitazone.
- c. Fasting levels of serum glucose and insulin. We will obtain serum levels of fasting glucose and insulin every four weeks in all patients receiving pioglitazone

Secondary End points

- a. Objective response (OR) is the proportion of patients with confirmed complete response (CR) or confirmed partial response (PR) according to the Response Evaluation Criteria in Solid Tumors (RECIST). Progression free survival (PFS) and overall survival (OS) of patients on treatment with pioglitazone.
- b. Changes in weight in patients with pancreas cancer receiving pioglitazone.
- c. Changes in ECOG performance status in patients with pancreas cancer receiving pioglitazone.
- d. Changes in symptoms and quality of life using the FACT-Hep questionnaire, version 4 (see Appendix 4).
- e. Characterize MRI determined changes in a) pancreatic intratumor fat; and b) body fat distribution in pancreatic cancer patients treated with pioglitazone (pilot study on 8-10 patients chosen by PI/investigator discretion) (UT Southwestern and PHS patients ONLY).
- f. Compare changes in serum and MRI end points between pioglitazone and control arms.

VIII. Study Design

Study Arm:

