Monitoring for multi-institutional studies conducted with SCC as the primary site and coordinating center are the responsibility of the DOT Clinical Research Manager (CRM). The CRM or designee monitors all sub-sites for safety and data quality. The purpose of ongoing data monitoring at sub-sites is to ensure regulatory compliance, adherence to protocol requirements, and patient safety.

Sub-sites will be monitored no less than annually. Monitoring on site is preferred; however, remote monitoring is acceptable where there is not adequate funding for travel. The research documentation for at least 5 subjects is reviewed each time a study is monitored.

Monitoring will include verification of source documentation regarding consent, patient eligibility, investigational treatment, drug accountability, serious adverse events, toxicities, and treatment response. Results of data monitoring of sub-sites will be documented and the results will be made available to the QAC, during trial audit.

SAE's and reportable AE's must be reported to the IRB of the institution in which they occurred, the SCC lead investigators, and the SCC DSMC. The DOT Manager or lead coordinator ensures that the PIs at all of the participating sites and the respective IRBs are notified of the events and resulting action for events which modify the risk of the protocol or which otherwise meet FDA requirements for expedited reporting.

XX. **Data analysis and Statistical Methods**

A. **Study Design and Sample Size**

This is a double arm, open label, Phase II study of pioglitazone in patients with pancreatic cancer. The primary endpoint for the sample size calculation is the adiponectin serum levels change after the pioglitazone treatment, which is the main indicator for insulin response improvement. We are interested in testing the hypothesis that pioglitazone can increase adiponectin by 40% from baseline. The change of adiponectin from baseline was defined as $c=(x_1-x_0)/x_0$, where x_1 is the adiponectin level after treatment, and x_0 is the baseline adiponectin level. So the adiponectin

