change is a continuous variable. The null hypothesis is that there is no change of adiponectin level. ($H_0: c=0$). The alternative hypothesis is that the treatment will lead to 40% change of adiponectin from baseline ($H_1: c=0.4$). Assuming that the standard deviation of the change is 0.5, (i.e the standard deviation of c values across population is 0.5), that a sample of 15 patients will provide a power of 82% at a significance level of 0.05 to detect 40% changes from baseline. This sample size calculation was implemented using SAS, and was reproduced using Power and Sample Size (PS) software.

B. *Statistical Analysis Plan*

Biomarkers analyses

Statistical graphical tools will be used to illustrate the biomarker changes over time. Mean and median changes of results for glucose tolerance test, serum adiponectin level test, weight changes, and ECOG performance status will be summarized. Pre-defined cut-offs will be used to dichotomize the patients into with or without insulin response improvement which consists changes in serum adiponectin levels and standard glucose tolerance test. The insulin response improvement rate and 95% exact confidence interval will be calculated.

Tumor response analyses

Complete response rate, partial response rate, objective response rate and progression rate after week 8 with the exact 95% confidence intervals will be provided.

Time to progression

For a given patient, time to progression will be defined as the number of days from the day of registration to the day the patient experiences an event of disease progression (or death). If a patient has not experienced an event of disease progression (or death) at the time of analysis, then the patient's data will be censored at the date of the last available evaluation. Progression-free survival will be summarized using the point estimate of the median time to progression, and the associated 90% confidence interval. Moreover, the proportion of patients who are progression free at 24 months (after entering the study) will be calculated and the 90% confidence interval for this proportion will be constructed. The data will be presented graphically using Kaplan-Meier plots. Additionally, exploratory analysis may be performed including multivariate Cox regression analysis with appropriate baseline characteristics as covariates.

Overall survival

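### The primary hypothesis rests on an unranked family of four markers, the only hypothesis test and power are for adiponectin alone, and the analysis plan contains neither that test nor a rule for which quantity decides

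*Combined protocol and SAP*

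**What the plan says.** Four parts of the combined protocol and SAP bear on this point.

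- **V. Hypothesis:** "Our primary hypothesis is that patients with pancreas cancer will have significant improvements in markers of insulin resistance when treated with pioglitazone". The noun is plural, and nothing says whether one, some or all markers must improve.
- **VI. Objectives and VII. Endpoints:** The primary objective is descriptive: "Describe change in markers of insulin resistance, including in adiponectin levels standard glucose tolerance test, and serum levels of insulin and glucose". The endpoint section then says "The primary end point will be improvement in insulin resistance markers" and lists (a) adiponectin at baseline and after 8 weeks, (b) the OGTT at baseline and after 8 weeks, and (c) fasting glucose and insulin every four weeks. There is no ranking and no definition of improvement.
- **XX.A Study Design and Sample Size:** "The primary endpoint for the sample size calculation is the adiponectin serum levels change after the pioglitazone treatment". Adiponectin change is described there as the quantity "which is the main indicator for insulin response improvement". With c the relative change from baseline, the hypotheses are c = 0 and c = 0.4. The assumed SD is 0.5, and 15 patients give 82% power at 0.05.
- **XX.B, Biomarkers analyses:** Mean and median changes are summarised for the OGTT, adiponectin, weight and ECOG status. Then: "Pre-defined cut-offs will be used to dichotomize the patients into with or without insulin response improvement which consists changes in serum adiponectin levels" and OGTT. "The insulin response improvement rate and 95% exact confidence interval will be calculated". The cut-offs are not given, and neither is a rule for combining the two components. Fasting glucose and insulin do not appear in this paragraph. They return only as explanatory variables in the regressions under Correlative Analyses.

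**The concern.** The endpoint section, the sample-size section and the analysis plan work with three different quantities: a four-marker family, adiponectin alone, and an adiponectin-plus-OGTT responder. Two consequences follow.

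First, the powered test is missing from the analysis plan. An analyst who followed XX.B to the letter would never test c = 0, the hypothesis for which the 15 patients were chosen.

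Second, the answer to the primary question depends on which section is read. If fasting insulin improved clearly and adiponectin did not, section VII would permit a favourable conclusion and XX.A would not. The study is open label, so that choice could be made after the marker results are known. The 0.05 level in XX.A covers one marker and gives no protection to a claim drawn from the family.

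**Working it through.** **1. Reproduce the plan's own figure.** Inputs from XX.A: effect 0.4, SD 0.5, n = 15, level 0.05 (sidedness not stated).

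- Standardised effect = 0.4 / 0.5 = 0.8.
- Noncentrality = 0.8 × √15 = 3.098, with 14 degrees of freedom.
- A two-sided one-sample t-test has critical value 2.145 and power 82.1%, which agrees with the stated 82%.
- A one-sided t-test would give 90.3% and a two-sided normal approximation 87.3%. Neither matches.

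The power statement is therefore correct for a two-sided one-sample t-test on adiponectin alone at an unadjusted 0.05.

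**2. Compare the sections.**

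| Section | Quantity | Called primary? | Test or success rule |
|---|---|---|---|
| V, VII | Adiponectin, OGTT, fasting glucose, fasting insulin | Yes | None |
| XX.A | Adiponectin change | Yes, for the sample size calculation | c = 0 against c = 0.4, level 0.05 |
| XX.B | Responder from adiponectin and OGTT | No | Exact 95% interval only; no cut-offs, no reference rate |

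**3. Size of the selection risk.** The documents do not say that each marker is tested or that any one is enough. Assume both, with each marker tested at two-sided 0.05 and so a 2.5% chance of a false result in the favourable direction. For k independent looks, the chance of at least one is 1 − (1 − 0.025)^k.

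- Four markers at week 8: 1 − 0.975^4 = 9.6%.
- Six looks, the most that section VII allows (adiponectin and OGTT at week 8; fasting glucose and fasting insulin at weeks 4 and 8): 1 − 0.975^6 = 14.1%.

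Markers from the same patients will be correlated, and the documents give no correlation. Simulating one-sample t-tests with n = 15 and equal pairwise correlation (at least 200,000 trials per setting) gives:

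| Looks | Independent | Correlation 0.5 | Correlation 0.9 |
|---|---|---|---|
| 1 | 2.5% | 2.5% | 2.5% |
| 4 | 9.6% | about 8% | about 5% |
| 6 | about 14% | about 11% | about 6% |

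**4. Compare the remedies.**

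- Adiponectin as sole primary: level 0.05, power 82.1%, n = 15.
- All four markers kept as primary with a Bonferroni correction: 0.05 / 4 = 0.0125 each. Power for adiponectin falls to 60.0%, and n = 22 is the smallest size that restores at least 82%.

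**The case against.** The strongest reply is that the plan already points to adiponectin. XX.A gives it the leading role, and the only hypotheses in the documents concern it. The primary objective is to describe, the study is called exploratory and a pilot, and XX.B schedules no per-marker tests. On this view the error rates above belong to a procedure nobody planned. The plural in section V could equally mean that all markers must improve, which would put the false-positive rate below 2.5%.

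Much of this stands. It is why the percentages are conditional and why the point is a clarification the plan should make, not a fatal flaw. It does not close the gap. The adiponectin label is tied to the sample size calculation and is not carried into VII or XX.B. Section V still predicts significance, and a plan that claims power at 0.05 should say what that 0.05 governs. That the plural can be read as any or as all is itself the ambiguity.

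Three stronger readings are tempting but not supported:

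- **That three sections name three different primaries.** Only VII and XX.A use the word for an endpoint. The XX.B responder is never called primary.
- **That any marker at week 4 or week 8 could carry the claim.** Eight looks would give 1 − 0.975^8 = 18.3%. But VII fixes week 8 for adiponectin and the OGTT and leaves only the fasting measures at four-weekly visits, so six is the most it allows. XVI and the visit schedule do list week-4 draws of adiponectin and the OGTT, but a measurement schedule does not define the endpoint.
- **That the false-positive rate is several times nominal whatever the correlation.** At correlation 0.9 it is about double for four markers.

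**Conclusion.** The concern holds in this form: the primary hypothesis is stated on an unranked four-marker family, the only test and power apply to adiponectin, the analysis plan omits that test and leaves two of the four primary markers out of its biomarker analysis, and no section says which quantity decides. These conclusions follow from the text alone.

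The size of the risk rests on two assumptions, an any-marker rule at two-sided 0.05 and a correlation the documents do not give. Under them, a false favourable claim has a chance of roughly 5% to 10% for the four markers at week 8 and 6% to 14% for six looks, against 2.5% for one marker. A reader should not infer that the stated power is wrong, since it reproduces, or that the plan commits to testing every marker. The plan should be corrected before analysis, at a severity tempered by the study's exploratory purpose.

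**What to change.** Change the wording in three places.

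- **VII:** name the relative change in serum adiponectin from baseline to week 8, as defined in XX.A, as the single primary endpoint. Make the OGTT, fasting glucose, fasting insulin and the responder rate secondary.
- **XX.B:** add the two-sided 0.05 one-sample t-test of c = 0 that the 82% power assumes. Report each secondary marker with its estimate and 95% interval. State the responder cut-offs and how the adiponectin and OGTT components combine.
- **V:** limit the word significant to the adiponectin test.

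The sample size stays at 15 and the power at 82%, with no new data collection. The small cost is that the other markers cannot support the primary claim on their own. They are still fully reported. A fixed testing order for the secondary markers is possible but not needed to resolve this point.
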